## 16.0 Potential Benefits to Subjects\*

16.1 *Describe the potential benefits that individual subjects may experience from taking part in the research. Include as may be*

**PROTOCOL TITLE: Development and Evaluation of a Tonic Immobility Focused Psychoeducational Intervention - RCT**

*useful for the IRB's consideration, the probability, magnitude, and duration of the potential benefits.*

The primary benefits to participants include possible improvements to mental health.

**16.2** *Indicate if there is no direct benefit. Do not include benefits to society or others.*

N/A

**17.0 Data Management\* and Confidentiality**

**17.1** *Describe the data analysis plan, including any statistical procedures or power analysis.*

Preliminary analyses and data screening will be conducted prior to the primary analyses. This will include checking equivalence of random assignment to treatment condition based on key baseline characteristics. Specifically, analyses will be conducted to ensure that there are not baseline differences between condition (active vs. control) in terms of age, gender, and TIQ total scores.

Hierarchical linear regression analyses will be conducted to examine the impact of intervention condition on early treatment outcomes including posttreatment guilt, posttreatment shame, and week 1 PTSD symptoms. Analyses will be conducted in SPSS version 27.0.

Latent difference score analyses will be utilized to examine the differential change in guilt, shame, and PTSD symptoms between intervention conditions, across all study timepoints. Analyses will be conducted in Mplus version 8.0 (Muthén & Muthén, 1998-2017). Full information maximum likelihood (FIML) with the adjusted Yuan-Bentler scaled chi-square index (Y-B  $\chi^2$ ) will be utilized when possible in order to account for missing data. To determine model fit, the S-B  $\chi^2$  statistic as well as several indices will be used.

Three separate models will be estimated for the impact of treatment condition on guilt, shame, and PTSD symptoms. The effects of treatment condition on changes in guilt from pre-intervention to post-intervention (change 1), from post-intervention to week 1 (change 2), and from week 1 to month 1 (change 3) will be examined using a multi-group latent difference score (LDS) approach (Mun et al., 2009). The same methods will be used to examine effects of treatment condition on shame from pre-intervention to post-intervention (change 1), from post-intervention to week 1 (change 2), and from week 1 to month 1 (change 3) and PTSD symptoms from pre-intervention to week 1 (change 1), and from week 1 to month 1 (change 2).

The indirect effects of treatment condition on PCL-5 scores at month 1 through week 1 guilt and shame will be examined in two separate

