## PROTOCOL TITLE: Development and Evaluation of a Tonic Immobility Focused Psychoeducational Intervention - RCT

6.2 The study proposes to enroll 120 participants to test the efficacy of the TIP intervention, compared to a HET control condition. All data collection will be conducted using Qualtrics. The study will be comprised of a total of three time points: Baseline, Week 1 follow-up, and Month 1 follow-up.

First, eligible participants will read and sign an informed consent that outlines all study procedures, details limits to confidentiality, and emphasizes that participants may discontinue participation at any time with no penalty.

The first appointment, baseline, will include pre-intervention self-report measures, the completion of one of the two interventions (TIP or PHET), and post-intervention self-report measures. The baseline appointment is expected to take 90 minutes. Participants will be compensated with a \$30 gift card or 1.5 course credits. All baseline procedures will be conducted either in-person within the Anxiety and Behavioral Health Clinic research suite or virtually via HIPAA-compliant Zoom. For in-person sessions, all COVID-19 related federal, state, and local guidelines as well as FSU IRB regulations will be followed. See section 6.3 for further information on COVID-19 safeguards.

The second and third appointments, week 1 and month 1 follow-up, will be completed online. Participants will be contacted via email and asked to complete a battery of self-report measures via a Qualtrics survey link. The questionnaire is expected to last 30 minutes and participants will be compensated either a \$10 gift card or 0.5 course credits for the completion of each appointment.

After the completion of the month 1 follow-up appointment, participants will be debriefed and individuals in the control condition will be given the opportunity to receive the active treatment condition.

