## **14.0 Withdrawal of Subjects\***

*14.1 Describe anticipated circumstances under which subjects will be withdrawn from the research without their consent.*

Possible reasons for removal include failure to complete the TIP intervention or self-report measures.

*14.2 Describe procedures that will be followed when subjects withdraw from the research, including partial withdrawal from procedures with continued data collection.*

The participant will be told they can leave the research at any time and it will not be held against them. All data collected prior to withdrawal will be securely stored and analyzed unless otherwise requested. Participants will be able to contact the PI to request the removal of their data, if so desired.

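### The week 1 PCL-5 regression can use only survey responders, and neither it nor the planned FIML model is given the post-intervention guilt and shame scores that could correct for selective non-response

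*Combined protocol and SAP*

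**What the plan says.** Section 17.1 sets out two analyses of the arm effect on PTSD symptoms at week 1.

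- **Regression.** "Hierarchical linear regression analyses will be conducted to examine the impact of intervention condition on early treatment outcomes", the outcomes being "posttreatment guilt, posttreatment shame, and week 1 PTSD symptoms". The software sentence is "Analyses will be conducted in SPSS version 27.0". No missing-data method is given and the covariates in each step are not listed.
- **Latent difference score model.** The PTSD model, in Mplus, covers "PTSD symptoms from pre-intervention to week 1 (change 1), and from week 1 to month 1 (change 2"). The estimator is "Full information maximum likelihood (FIML) with the adjusted Yuan-Bentler scaled chi-square index", which "will be utilized when possible in order to account for missing data". Guilt, shame and PTSD symptoms each have their own model, so the PTSD model as described contains PCL-5 scores only.

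Section 6.2 explains how week 1 data arrive: "Participants will be contacted via email and asked to complete a battery of self-report measures via a Qualtrics survey link". It also places the post-intervention measures inside the baseline appointment, before anyone can be lost to follow-up. Section 2.2 hypothesises that reduced guilt and shame mediate the effect of condition on PTSD symptoms.

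The plan gives no expected dropout rate, no sensitivity analysis for missing data, and no statement of which week 1 PTSD result governs.

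**The concern.** An ordinary linear regression cannot use a person whose outcome is missing unless imputation or a likelihood method is specified, and none is. The week 1 PCL-5 regression therefore rests on responders, while change 1 of the Mplus model can also draw on people with only a baseline score. One question gets two answers from two sets of people.

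The more important gap is shared by both analyses. If people whose guilt was not relieved by TIP are less likely to answer the email, the TIP responders look better than the TIP arm as a whole. The scores that would reveal and correct this are already in hand for people who do not reply, but neither PTSD analysis is described as using them. The estimated benefit of TIP on PTSD symptoms would then be somewhat too large.

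**Working it through.** **1. Who enters the regression.** The documents give N = 120 but no dropout rate or allocation ratio. I assume 60 per arm. At 12% and 23% week 1 loss the regression uses 120 × 0.88 ≈ 106 and 120 × 0.77 ≈ 92 people. A FIML model can use everyone with a baseline score.

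**2. Size by hand.** If loss depends on guilt in one arm only, the complete-case bias (with baseline PCL-5 in the model) is approximately β × δ. Here β is the slope of week 1 PCL-5 on post-intervention guilt given baseline PCL-5, and δ is the shift in mean guilt among TIP responders, adjusted for baseline. Assumed correlations are 0.6 (baseline with week 1), 0.5 (guilt with week 1) and 0.4 (guilt with baseline).

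β = (0.5 − 0.6 × 0.4) / (1 − 0.4²) = 0.26 / 0.84 = 0.31

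A bias of 0.03 to 0.06 SD therefore needs δ of 0.03/0.31 ≈ 0.10 to 0.06/0.31 ≈ 0.19 SD, which is a modest degree of selection.

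**3. Simulation with loss related to guilt in the TIP arm.** Assumptions: 60 per arm, true effect −0.15 SD, correlations 0.6 (baseline with week 1), 0.7 (week 1 with month 1) and 0.5 (guilt with week 1), half of week 1 non-responders also missing month 1, 600 trials per setting. Entries are bias in SD; negative favours TIP. Monte Carlo error is about 0.007 to 0.009.

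| Missing at week 1 | Regression, no baseline | Regression, with baseline | FIML, PCL-5 only | FIML plus guilt |
|---|---|---|---|---|
| 12% | −0.05 | −0.03 | −0.02 | 0.00 |
| 20% | −0.09 | −0.05 | −0.04 | 0.00 |
| 32% | −0.15 | −0.07 | −0.05 | −0.01 |
| 18%, random | −0.01 | 0.00 | 0.00 | 0.00 |

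How far FIML on PCL-5 alone helps depends on who comes back at month 1. In a second set of 600 trials per setting, with 23% missing:

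- Non-responders also miss month 1: −0.048 (regression with baseline) against −0.055 (FIML, PCL-5 only).
- All return at month 1: −0.045 against −0.020.

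A further run at 12% to 23% loss gave −0.03 to −0.06 for both analyses and about 0.00 once guilt was added. The SD of the estimate was about 0.15 to 0.17 throughout, so adding guilt costs no precision.

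**4. Other mechanisms.** 1,500 trials per setting, true effect −0.4 SD, 20% to 22% missing at week 1:

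| Loss depends on | Regression, no baseline | Regression, with baseline | FIML, PCL-5 only |
|---|---|---|---|
| Nothing (random) | 0.00 | 0.00 | 0.00 |
| Baseline PCL-5, same in both arms | −0.01 | 0.00 | 0.00 |
| Baseline PCL-5, opposite by arm | −0.24 | 0.00 | 0.00 |
| Unseen week 1 score, opposite by arm | −0.38 | −0.26 | −0.25 |
| Month 1 score (observed), opposite by arm | −0.27 | −0.15 | 0.00 |

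Entering baseline PCL-5 matters, and the plan does not say that it is entered. Month 1 PCL-5 is a useful auxiliary. Neither method corrects loss driven by the missing value itself.

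**5. Scale.** Against a standard error of 0.15 to 0.17, the bias is 0.03/0.17 ≈ 0.18 to 0.06/0.15 = 0.40 standard errors. As a share of the assumed −0.15 SD effect it is 0.03/0.15 = 20% to 0.06/0.15 = 40%. That share depends on an effect size the plan does not state.

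**The case against.** The strongest counter-argument is that the plan already has a FIML model for this contrast and that the bias is an assumption. Part of that stands. The dropout rate, correlations, effect size and arm-specific mechanism are all assumed, and random or similar loss in both arms gives no material bias. But the planned PTSD model contains only PCL-5 scores, so it shares much or all of the bias when guilt drives the loss.

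A reader might infer four stronger things that the documents do not support.

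- **That only the SPSS regression is exposed.** The tables show otherwise: with baseline entered, the two analyses are often about equally biased or equally unbiased. Omitting guilt and shame is the source, not the choice of software.
- **That the regression contradicts section 14.2.** That section says "All data collected prior to withdrawal will be securely stored and analyzed unless otherwise requested". It does not require every model to include every person, and those data can enter the other models.
- **That the Mplus models certainly retain everyone.** FIML is qualified as used where possible, and section 14.1 allows removal for not completing TIP or the self-report measures. Listwise deletion in SPSS is likewise not stated; it follows from the absence of any other method.
- **That all three early-outcome regressions are affected.** Post-intervention guilt and shame are collected at the baseline appointment, so a missed email cannot remove them.

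**Conclusion.** The concern holds as a modest, avoidable weakness. The week 1 PCL-5 regression has no missing-data method and can use only responders. The overlapping FIML model does not repair this, because neither analysis is described as using post-intervention guilt and shame. With 60 per arm and 12% to 23% loss related to guilt in the TIP arm only, both favour TIP by about 0.03 to 0.06 SD, with FIML nearer 0.02 when non-responders return at month 1. This is less than half a standard error. Adding guilt brings the bias to about zero under that mechanism. With random or similar loss there is nothing to correct. If loss depends on the unseen week 1 score, the proposed change should not be relied on to remove the bias. The plan also leaves open which of its two week 1 PTSD estimates governs.

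**What to change.** In section 17.1:

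1. Fit the week 1 PCL-5 regression by FIML in Mplus, with baseline PCL-5 and condition as predictors and with post-intervention guilt, post-intervention shame and month 1 PCL-5 as auxiliary variables.
2. Add post-intervention guilt and shame as auxiliaries to the PTSD latent difference score model.
3. Keep the complete-case regression as a labelled sensitivity analysis.
4. State which week 1 PTSD estimate governs.

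The post-intervention guilt and shame regressions can stay in SPSS. The auxiliaries are the substance of the change: moving to FIML with only condition and baseline PCL-5 in the model would give the same answer as complete cases.

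The cost is a few sentences of analysis wording. The measures, software and estimator are already in the plan, and no new data or visits are needed. The change should be settled before outcomes are examined by arm.

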## 1.0 Study Summary

Study Title	Development and Evaluation of a Tonic Immobility Focused Psychoeducational Intervention - RCT
Study Design	Randomized Controlled Trial
Primary Objective	To evaluate the efficacy of a brief-web-based intervention (Tonic Immobility Psychoeducation; TIP) intended to educate about tonic immobility (TI) within a sample of those who experienced TI in the context of a traumatic event.
Secondary Objective(s)	(1) TIP will significantly reduce feelings of posttraumatic feelings of guilt and shame compared to control (2) TIP will significantly reduce PTSD symptoms across time relative to control (3) Reduction in trauma-related guilt and shame will mediate the association between condition and changed in PTSD symptoms at follow-up.
Research Intervention(s)/Investigational Agent(s)	Tonic Immobility Psychoeducation Health Education Training
IND/IDE #	
Study Population	Adults who endorse prior TI during a traumatic event and elevated PTSD symptoms
Sample Size	120
Study Duration for individual participants	1 month
Study Specific Abbreviations/Definitions	TI = Tonic Immobility TIP = Tonic Immobility Psychoeducation HET = Health Education Training PTSD = Posttraumatic Stress Disorder

PROTOCOL TITLE: Development and Evaluation of a Tonic Immobility Focused Psychoeducational Intervention - RCT

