## 2.0 Objectives\*

- 2.1 A randomized controlled trial is planned to evaluate a brief, web-based intervention intended to educate about tonic immobility (TI) within a sample of those who experienced TI in the context of a traumatic event.
- 2.2 It is hypothesized that the TIP intervention will show benefits in a sample of those who have experienced a traumatic event. Specifically, we hypothesize that: TIP will significantly reduce feelings of posttraumatic feelings of guilt and shame compared to control; TIP will significantly reduce PTSD symptoms across time relative to control; reduction in trauma-related guilt and shame will mediate the association between condition and changed in PTSD symptoms at follow-up.

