## PROTOCOL TITLE: Development and Evaluation of a Tonic Immobility Focused Psychoeducational Intervention - RCT

mediation models. Maximum likelihood and percentile bootstrapped CIs (with 5,000 resamples) will be used (Hayes & Scharkow, 2013; Preacher & Hayes, 2004).

17.2 *Describe the steps that will be taken to secure the data (e.g., training, authorization of access, password protection, encryption, physical controls, certificates of confidentiality, and separation of identifiers and data) during storage, use, and transmission.*

All data will be coded by arbitrary participant numbers to ensure confidentiality and will be stored using password protected documents. Specifically, once the participant is consented, they will be assigned a unique study ID, which will be used instead of their name on subsequent surveys. The document linking participant names to study IDs will be recorded in a password-protected Microsoft Excel document, which will be stored on a password-protected server inside the Anxiety and Behavioral Health Clinic (ABHC) research suite. Only ABHC study staff (i.e., PI, graduate students, and project coordinators) who have been trained in data management procedures will be able to access the data via password.

17.3 *Describe any procedures that will be used for quality control of collected data.*

See 17.4

17.4 *Describe how data or specimens will be handled study-wide:*

Data entry personnel will download the data into a dedicated, password-protected computer database. Computer files will be maintained on the servers and backed up daily. Computers and databases will be password protected with independent passwords known only to the PI and data entry personnel. Other safeguards include: (a) ensuring that all project staff are well informed about regulations pertaining to confidentiality, (b) the use of ID numbers as opposed to names on all data forms, (c) utilizing computer-based assessments whenever possible.

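### No analysis is designated primary and no alpha or multiplicity rule is stated; none of the listed between-arm comparisons is explicitly a test of the pre-intervention to month 1 difference

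*Combined protocol and SAP*

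**What the plan says.** - **Objectives (1.0 Study Summary, 2.0).** The primary objective is "To evaluate the efficacy of a brief-web-based intervention (Tonic Immobility Psychoeducation; TIP"), with no outcome measure or time point attached. The hypotheses on guilt and shame, PTSD symptoms and mediation appear in the Study Summary as secondary objectives, unranked. The PTSD hypothesis reads "TIP will significantly reduce PTSD symptoms across time relative to control", with neither a time point nor a significance level.
- **Endpoints (4.0).** This section says when recruitment and data collection end and that there are no safety endpoints. It names no efficacy endpoint.
- **Regressions (17.1).** The section opens with "Preliminary analyses and data screening will be conducted prior to the primary analyses" but does not say which analyses those are; the phrase may only mean the main ones. Regressions then cover "early treatment outcomes including posttreatment guilt, posttreatment shame, and week 1 PTSD symptoms".
- **Change models (17.1).** The effect of condition on three successive changes in guilt "will be examined using a multi-group latent difference score (LDS) approach". Shame is handled the same way. For PTSD symptoms there are two changes: "PTSD symptoms from pre-intervention to week 1 (change 1), and from week 1 to month 1 (change 2".
- **Mediation (17.1).** "The indirect effects of treatment condition on PCL-5 scores at month 1 through week 1 guilt and shame" are examined in two models. For these, "Maximum likelihood and percentile bootstrapped CIs (with 5,000 resamples) will be used".
- **Schedule (6.2).** Month 1 is the last assessment.

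**The concern.** The hypotheses claim significant benefit, yet the plan offers several unranked routes to that claim: three outcomes, several intervals and two kinds of model. Whichever result is favourable could be presented as the efficacy result, and a reader could not tell whether it was chosen afterwards. Nothing limits the overall chance of a false positive.

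The choice of intervals adds a second problem. A benefit that builds gradually is split between two changes and may be significant in neither while being significant overall. A benefit that appears early and partly fades may give a significant first change and a non-significant second one, leaving it open whether anything remains at month 1. In both cases the informative quantity is the arm difference from pre-intervention to month 1, and the plan does not list a test of it.

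**Working it through.** **Inputs.** From the documents: N = 120 (6.2) and the list of analyses (17.1). Assumed, because the documents give no figure: 60 per arm, complete data, two-sided 0.05, SD 1 at each visit, correlation 0.5-0.7 between visits and 0.4-0.8 between outcomes, and regressions adjusted for the outcome's own baseline.

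**1. The plan's own figure.** N = 120 comes without alpha, power or effect size, so it cannot be reproduced. For scale, 60 per arm has 80% power for one contrast at (1.960 + 0.842) × √(2/60) = 0.51 SD.

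**2. Count.** 3 regressions + (3 + 3 + 2) changes = 11 between-arm comparisons. The 3 regressions largely repeat change 1, leaving about 8 distinct. Two indirect effects bring the list to 13.

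**3. Which of them covers pre-intervention to month 1?**

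| Outcome | Regression | Changes compared between arms | Month 1 score as outcome |
|---|---|---|---|
| Guilt | post-intervention | pre-post, post-week 1, week 1-month 1 | none |
| Shame | post-intervention | pre-post, post-week 1, week 1-month 1 | none |
| PTSD symptoms | week 1 | pre-week 1, week 1-month 1 | mediation models only; indirect effects listed |

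No row contains the full interval as a listed test.

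**4. Chance of at least one false positive with no true effect.** If the tests were independent, 1 − 0.95^11 = 43% and 1 − 0.95^8 = 34%. The tests are correlated, so the rates were simulated (27 correlation settings, 20,000 trials each):

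| Tests | Any significant | In TIP's favour |
|---|---|---|
| All 11, changes tested singly | 27-35% | 15-21% |
| The 8 changes alone, singly | 24-32% | 14-18% |
| One joint test per outcome model | 10-14% | – |
| Joint tests plus the 3 regressions | 17-22% | – |
| One named primary | 5% | about 2.5% |

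**5. Power when a 0.5 SD PCL-5 effect accrues evenly (0.25 SD per interval).** SD of change = √(2(1 − r)), and noncentrality = effect / (SD × √(2/60)). Example with r = 0.5: SD = 1, each segment 0.25/0.1826 = 1.37, the sum 0.5/0.1826 = 2.74. If the correlation across the full interval decays to r² = 0.25, the SD of the summed change is 1.225 and its noncentrality 2.24.

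| Adjacent correlation | 0.5 | 0.6 | 0.7 |
|---|---|---|---|
| Each segment | 27% | 33% | 42% |
| Joint 2-df test, equal correlation | 68% | 78% | 89% |
| Joint 2-df test, decaying correlation | 49% | 56% | 67% |
| Summed contrast, equal correlation | 78% | 86% | 94% |
| Summed contrast, decaying correlation | 60% | 67% | 77% |

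The sum is significant with neither segment significant in 29/27/21% of trials (equal) or 17/15/13% (decay).

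**6. Can a reader recover the month 1 result from the reported changes?** The point estimate, yes: it is their sum. The interval, no, because the variance of the sum needs Cov(change 1, change 2) = 2ρ − 1 − ρ₁₃, where ρ is the adjacent correlation and ρ₁₃ the pre-to-month-1 correlation. At ρ = ρ₁₃ = 0.5 this is −0.5, so the variance of the sum is 1 + 1 − 1 = 1. Leaving the covariance out would give 2.

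**7. Benefit of 0.5 SD at week 1, half lost by month 1.** Change 1 is significant and change 2 is not in 52-56% of trials. The month 1 effect is then 0.25 SD, for which the summed contrast has 27-42% power (equal) or 20-27% (decay).

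**The case against.** Several points on the other side are sound.

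- **Time points and contrasts are named.** A reader might infer that the plan specifies none. That is not so: 17.1 gives the outcome and interval of every change and the outcome and time of every regression. Only the designation of one as primary is missing.
- **Month 1 is not wholly untested for PCL-5.** A reader might infer that the arm difference at the last visit will have no interval or test at all. The documents do not support that for PCL-5. The mediation models have month 1 PCL-5 as their outcome, so a total effect could be read from them, and the bootstrap intervals are not expressly confined to the indirect path. But the total effect is not listed as a test and no adjustment for baseline PCL-5 is stated. Guilt and shame have no such route.
- **The general aim in 17.1 covers change over all the assessments.** That could accommodate an overall test. It does not define one; the models then described use adjacent intervals.
- **The changes may be tested jointly.** The plan does not say. If they are, the false-positive rate is 10-14% rather than 27-35%, and for a gradual benefit the joint test loses about 5-11 points of power against the sum, far less than the single-segment figures suggest. Equal accrual over one week and the rest of the month after one 45-minute session is itself only an assumption.
- **Adjacent-interval modelling is legitimate.** This stands. The point is what is missing beside it.

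**Conclusion.** The concern holds in this form: no analysis is designated primary, no alpha or multiplicity rule is given, and no listed comparison is explicitly a test of the pre-intervention to month 1 arm difference. These are facts of the text and do not depend on the calculations.

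The size is illustrative, since the correlations, effect size, allocation ratio and dropout are all assumed. Like is to be compared with like: 27-35% (singly) or 10-14% (jointly; 17-22% with the regressions) against 5%, or 15-21% against 2.5% when only results in TIP's favour count. A reader might set 27-35% against 2.5%, or take it as the plan's actual error rate. Neither is supported, because the first mixes two-sided and one-direction rates and the second presumes single testing. A benefit wholly lost by month 1 is not part of the concern, because change 2 would normally show it. This is a cheap improvement, not a flaw that invalidates the trial.

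**What to change.** Before outcome data are examined by arm, amend 4.0 and 17.1 as follows. Without that deadline, a primary named late would not remove the risk of selective presentation.

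1. Name one primary outcome, time point and contrast at a stated two-sided alpha. The choice is the sponsor's. One example is the arm difference in PCL-5 change from pre-intervention to month 1, obtained as change 1 + change 2 in the existing latent-difference model, with its 95% CI.
2. Add the summed contrast (changes 1 + 2 + 3) for guilt and for shame, tested after the primary in fixed order or with Holm. Testing all three sums side by side at 0.05 would give a 10-14% chance of any false positive.
3. State whether segment changes are tested singly or jointly, and label them descriptive. Label the regressions supportive and the mediation analyses secondary or exploratory.
4. If an early contrast is made primary, make the month 1 contrast the first secondary.

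**Cost.** Protocol wording and one derived parameter per existing Mplus model; no new data, visits or participants.

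**Downsides.**
- Segment results are no longer individually confirmatory.
- If a 0.5 SD benefit is complete by week 1 and held, and correlation decays, a month 1 primary has 60/67/77% power against 78/86/94% for change 1 (adjacent correlation 0.5/0.6/0.7, complete data). With 48 per arm at month 1 it falls to 51/57/67% on completers, or 56/63/73% with full-information likelihood.
- If the benefit is half lost by month 1, the summed contrast has only about 20-42% power. The gain there is the confidence interval rather than a significant result.

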**6.0 Procedures Involved\***

- 6.1 The study adheres to a randomized controlled trial (RCT) design. Participants will be randomized to either the TIP or HET condition. Randomization will be stratified based on undergraduate vs. community member status. For each group, a random number table will be generated in Excel with either 1 = TIP or 2 = HET assigned to each participant ID. After completion of consent, the participant will receive their ID (assigned in sequential order) and the research assistant will prepare the corresponding treatment.

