## PROTOCOL TITLE: Development and Evaluation of a Tonic Immobility Focused Psychoeducational Intervention - RCT

current investigation based on prior TI experience (TIQ items A & B) and elevated posttraumatic stress symptoms (PCL-5). Exclusion criteria includes individuals who have not endorsed past TI behavior and are not 18 years or older.

*10.3 Indicate specifically whether you will include or exclude each of the following special populations: (You may not include members of the above populations as subjects in your research unless you indicate this in your inclusion criteria.)*

- *Adults unable to consent:* Excluded
- *Individuals who are not yet adult:* Excluded
- *Pregnant women:* Excluded
- *Prisoners:* Excluded

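### The mediation models in Section 17.1 name no pre-intervention covariates, so correlated baselines can produce apparent mediation where there is none

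*Combined protocol and SAP*

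**What the plan says.** Section 2.2 and secondary objective 3 in Section 1.0 state the hypothesis in terms of change: "reduction in trauma-related guilt and shame will mediate the association between condition and changed in PTSD symptoms at follow-up". Section 17.1 gives the analysis as "The indirect effects of treatment condition on PCL-5 scores at month 1 through week 1 guilt and shame", with one model for guilt and one for shame, maximum likelihood estimation and percentile bootstrap intervals from 5,000 resamples. No covariate is named, and none is excluded.

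Other parts of the plan bear on the point:

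- The latent difference score models in Section 17.1 start from pre-intervention for guilt, shame and PTSD symptoms, so all three baselines are collected.
- Age, gender and TIQ total appear in Section 17.1 only in a check of balance between arms.
- The hierarchical regressions cover early outcomes only, and their predictor blocks are not listed.
- Section 6.1 says: "Randomization will be stratified based on undergraduate vs. community member status". That stratum enters no stated model.
- Section 10.2 selects participants on elevated PCL-5 but gives no cut-off.

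**The concern.** An indirect effect is the product of two paths. The first, condition to week 1 guilt or shame, is randomised. The second, week 1 guilt or shame to month 1 PCL-5, is not. Participants who feel more guilt before treatment may also have more PTSD symptoms before treatment; Section 3.1 itself links tonic immobility to guilt, shame and PTSD symptoms together. If both scores carry over, week 1 guilt predicts month 1 PCL-5 within each arm even when changing guilt does nothing to PTSD symptoms. Balance between arms does not help, because the correlation exists inside each arm. The latent difference score models do not help either, because each handles one outcome on its own.

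If TIP then lowers guilt, as the first hypothesis expects, a real first path is multiplied by a spurious second path and the model reports mediation. The error arises when the first hypothesis succeeds, which is when a mechanism claim is most likely to be made. What is at stake is secondary objective 3, not the randomised comparisons on guilt, shame or PTSD symptoms.

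**Working it through.** The plan states no figure to reproduce here, so the check is a null simulation.

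**Inputs from the documents.** N = 120 (Section 6.2); two arms (Section 6.1); week 1 mediator, month 1 PCL-5 and percentile bootstrap (Section 17.1).

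**Assumptions.** Equal allocation, 60 per arm; 95% intervals; TIP effect on guilt *a* from 0 to 0.8 SD; baseline correlation *rb* from 0 to 0.6; stability of guilt *rg* and of PCL-5 *rp* from 0.5 to 0.7. For scale, 60 per arm detects (1.96 + 0.84) × √(2/60) = 0.51 SD with 80% power.

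**Model with zero true mediation.** G0 and P0 are pre-intervention guilt and PCL-5, and T is condition.

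- Week 1 guilt: G1 = rg·G0 + e − a·T
- Month 1 PCL-5: P2 = rp·P0 + e′ − d·T, with no G1 term

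**Expected bias.** With unit variance within arm, regressing P2 on T and G1 gives a G1 coefficient of rg·rp·rb. For stability 0.7 and rb = 0.5 this is 0.7 × 0.7 × 0.5 = 0.245 (simulated mean 0.249). The spurious indirect effect at a = 0.5 is −0.5 × 0.245 = −0.12 (simulated −0.125). The true value of both is zero.

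**Effect of selection.** If entry requires P0 above the screened mean:

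- Var(P0) falls to 1 − 2/π = 0.363
- Cov(G0, P0) = 0.5 × 0.363 = 0.182
- Var(G0) = 1 − 0.25 × 0.637 = 0.841
- within-sample r = 0.182/√(0.363 × 0.841) = 0.33
- G1 coefficient = 0.49 × 0.182/(0.49 × 0.841 + 0.51) = 0.097

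Selection therefore shrinks the bias but does not remove it.

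**Share of 95% intervals excluding zero** (1,000 trials per row, 1,000 resamples, Monte Carlo SE at most 1.6 points; d = 0 unless stated). The adjusted model adds G0, P0 and the stratum to both equations.

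| Entry | a (SD) | rb | rg / rp | Without | With |
|---|---|---|---|---|---|
| No selection | 0 | 0.5 | 0.7 / 0.7 | 2.9% | 0.1% |
| | 0.5 | 0 | 0.7 / 0.7 | 3.7% | 4.9% |
| | 0.3 | 0.3 | 0.7 / 0.7 | 10.6% | 2.3% |
| | 0.3 | 0.5 | 0.7 / 0.7 | 26.2% | 1.5% |
| | 0.5 | 0.3 | 0.7 / 0.7 | 24.2% | 7.2% |
| | 0.5 | 0.5 | 0.7 / 0.7 | 59.7% | 5.6% |
| | 0.5 | 0.5 | 0.7 / 0.7, d = 0.4 | 56.5% | 4.5% |
| | 0.5 | 0.5 | 0.5 / 0.7 | 34.8% | 3.5% |
| | 0.3 | 0.5 | 0.5 / 0.5 | 9.7% | 2.7% |
| | 0.5 | 0.5 | 0.5 / 0.5 | 19.7% | 4.9% |
| P0 above mean | 0.3 | 0.3 | 0.7 / 0.7 | 4.3% | 2.9% |
| | 0.3 | 0.5 | 0.7 / 0.7 | 9.1% | 3.1% |
| | 0.5 | 0.3 | 0.7 / 0.7 | 8.7% | 6.0% |
| | 0.5 | 0.5 | 0.7 / 0.7 | 16.9% | 4.7% |
| | 0.8 | 0.5 | 0.7 / 0.7 | 22.8% | 5.4% |
| | 0.5 | 0.5 | 0.5 / 0.5 | 6.6% | 4.9% |

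Under selection, rb is the correlation in the screened population.

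A separately programmed simulation without selection (600 trials, 800 resamples, stability 0.6 to 0.7, rb 0.3 to 0.6) gave 6–33% at 0.3 SD, 18–72% at 0.5 SD and 23–88% at 0.8 SD without baselines. With both baselines it gave 2–3%, 4–6% and 6–7%.

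**What adjustment does not cure.** With an added post-baseline confounder (residual correlation 0.3; a = 0.5, rb = 0.5, stability 0.7, no selection), the rate is 76% without and 86% with the baselines. If the baselines are only noisy indicators of a shared trait (loading 0.6 to 0.8), adjustment cuts the bias in the G1 coefficient from 0.36–0.65 to 0.21–0.29, yet 27–86% of intervals still exclude zero.

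**The case against.** Four points deserve weight.

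- **Silence is not exclusion.** Section 17.1 is short and lists covariates for no model, and a hypothesis about change makes a baseline-adjusted fit plausible. This stands as a description of the text. But adjusted and unadjusted fits can lead to opposite conclusions, and the plan leaves that choice open until the data are in hand.
- **The largest rates ignore selection, and state guilt may be less stable than 0.7.** This stands on size. At 0.5 SD, correlation 0.5 and stability 0.7, selection at 1 SD above the mean gave 8–10% without and 6–7% with baselines. With guilt stability 0.5, PCL-5 stability 0.7 and selection at the mean, the unadjusted rates were 10% (0.5 SD, r = 0.5), 6% (0.5 SD, r = 0.3) and 4% (0.3 SD, r = 0.5). In the other direction, selecting on a separate screening score correlated 0.8 with the baseline score gave 33–37% against 5%. The documents do not settle which case applies.
- **The fix does not secure the mechanism claim.** This is true: post-baseline confounding and poorly measured baselines remain. It is a reason to state the assumption, not to leave out a known and measured confounder.
- **The stratum was not shown to help.** This is correct: it was simulated as an inert 50/50 indicator. The case for including it is that randomisation was stratified by it and that students and community members may differ in both scores.

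**Conclusion.** The concern holds. Followed literally, Section 17.1 fits mediation models whose mediator-to-outcome path is open to confounding by baselines that the trial already collects. The direction is clear: when TIP moves guilt or shame and the baselines are correlated, false mediation becomes more likely. The size is not determined by the documents. Across the assumed inputs with a TIP effect of 0.3 to 0.5 SD and correlated baselines, the false-positive rate runs from about nominal (4%) to 60% at correlations up to 0.5, and to 72% at a correlation of 0.6. With entry above the screened mean and stability 0.7 it is 4–17%. There is no inflation if TIP does not move guilt or if the baselines are uncorrelated. Adjustment brings every case with baseline confounding alone to 0–7%. Only the mechanism conclusion is affected. It should be corrected before analysis.

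**What to change.** State in Section 17.1 that pre-intervention guilt (or shame), pre-intervention PCL-5 and the undergraduate/community stratum are covariates in both the mediator and the outcome equation of each mediation model. Keep the percentile bootstrap with 5,000 resamples. Interpret the result as the indirect effect on baseline-adjusted month 1 PCL-5. This also fits the change-based hypothesis: with the baselines in both equations, the condition and mediator coefficients are the same whether scores or change from baseline are modelled.

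Add a sentence saying that other mediator-outcome confounding may remain, so the result supports a mechanism only if there is none. A sensitivity analysis for such residual confounding would strengthen this.

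The cost is one or two sentences for the models and the caveat, no new data, and three degrees of freedom per equation. The optional sensitivity analysis would need its own short specification.
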